182.402	Acute embolism and thrombosis of unspecified deep veins of left lower extremity
182.403	Acute embolism and thrombosis of unspecified deep veins of lower extremity, bilateral
182.409	Acute embolism and thrombosis of unspecified deep veins of unspecified lower extremity
182.41	Acute embolism and thrombosis of femoral vein
182.411	Acute embolism and thrombosis of right femoral vein
182.412	Acute embolism and thrombosis of left femoral vein
182.413	Acute embolism and thrombosis of femoral vein, bilateral
182.419	Acute embolism and thrombosis of unspecified femoral vein
182.42	Acute embolism and thrombosis of iliac vein
182.421	Acute embolism and thrombosis of right iliac vein
182.422	Acute embolism and thrombosis of left iliac vein
182.423	Acute embolism and thrombosis of iliac vein, bilateral
182.429	Acute embolism and thrombosis of unspecified iliac vein
182.43	Acute embolism and thrombosis of popliteal vein
182.431	Acute embolism and thrombosis of right popliteal vein
182.432	Acute embolism and thrombosis of left popliteal vein
182.433	Acute embolism and thrombosis of popliteal vein, bilateral
182.439	Acute embolism and thrombosis of unspecified popliteal vein
182.44	Acute embolism and thrombosis of tibial vein

182.441	Acute embolism and thrombosis of right tibial vein
182.442	Acute embolism and thrombosis of left tibial vein
182.443	Acute embolism and thrombosis of tibial vein, bilateral
182.449	Acute embolism and thrombosis of unspecified tibial vein
182.49	Acute embolism and thrombosis of other specified deep vein of lower extremity
182.491	Acute embolism and thrombosis of other specified deep vein of right lower extremity
182.492	Acute embolism and thrombosis of other specified deep vein of left lower extremity
182.493	Acute embolism and thrombosis of other specified deep vein of lower extremity, bilateral
182.499	Acute embolism and thrombosis of other specified deep vein of unspecified lower extremity
182.4Y	Acute embolism and thrombosis of unspecified deep veins of proximal lower extremity
182.4Y1	Acute embolism and thrombosis of unspecified deep veins of right proximal lower extremity
182.4Y2	Acute embolism and thrombosis of unspecified deep veins of left proximal lower extremity
I82.4Y3	Acute embolism and thrombosis of unspecified deep veins of proximal lower extremity, bilateral
I82.4Y9	Acute embolism and thrombosis of unspecified deep veins of unspecified proximal lower extremity
182.4Z	Acute embolism and thrombosis of unspecified deep veins of distal lower extremity
182.4Z1	Acute embolism and thrombosis of unspecified deep veins of right distal lower extremity
182.4Z2	Acute embolism and thrombosis of unspecified deep veins of left distal lower extremity
182.4Z3	Acute embolism and thrombosis of unspecified deep veins of distal lower extremity, bilateral
182.4Z9	Acute embolism and thrombosis of unspecified deep veins of unspecified distal lower extremity
182.5	Chronic embolism and thrombosis of deep veins of lower extremity
182.50	Chronic embolism and thrombosis of unspecified deep veins of lower extremity
182.501	Chronic embolism and thrombosis of unspecified deep veins of right lower extremity
182.502	Chronic embolism and thrombosis of unspecified deep veins of left lower extremity
182.503	Chronic embolism and thrombosis of unspecified deep veins of lower extremity, bilateral
182.509	Chronic embolism and thrombosis of unspecified deep veins of unspecified lower extremity
182.51	Chronic embolism and thrombosis of femoral vein
182.511	Chronic embolism and thrombosis of right femoral vein
182.512	Chronic embolism and thrombosis of left femoral vein
182.513	Chronic embolism and thrombosis of femoral vein, bilateral
182.519	Chronic embolism and thrombosis of unspecified femoral vein
182.52	Chronic embolism and thrombosis of iliac vein
182.521	Chronic embolism and thrombosis of right iliac vein
182.522	Chronic embolism and thrombosis of left iliac vein
182.523	Chronic embolism and thrombosis of iliac vein, bilateral
182.529	Chronic embolism and thrombosis of unspecified iliac vein

182.53	Chronic embolism and thrombosis of popliteal vein
182.531	Chronic embolism and thrombosis of right popliteal vein
182.532	Chronic embolism and thrombosis of left popliteal vein
182.533	Chronic embolism and thrombosis of popliteal vein, bilateral
182.539	Chronic embolism and thrombosis of unspecified popliteal vein
182.54	Chronic embolism and thrombosis of tibial vein
182.541	Chronic embolism and thrombosis of right tibial vein
182.542	Chronic embolism and thrombosis of left tibial vein
182.543	Chronic embolism and thrombosis of tibial vein, bilateral
182.549	Chronic embolism and thrombosis of unspecified tibial vein
182.59	Chronic embolism and thrombosis of other specified deep vein of lower extremity
182.591	Chronic embolism and thrombosis of other specified deep vein of right lower extremity
182.592	Chronic embolism and thrombosis of other specified deep vein of left lower extremity
182.593	Chronic embolism and thrombosis of other specified deep vein of lower extremity, bilateral
182.599	Chronic embolism and thrombosis of other specified deep vein of unspecified lower extremity
I82.5Y	Chronic embolism and thrombosis of unspecified deep veins of proximal lower extremity
I82.5Y1	Chronic embolism and thrombosis of unspecified deep veins of right proximal lower extremity
I82.5Y2	Chronic embolism and thrombosis of unspecified deep veins of left proximal lower extremity
I82.5Y3	Chronic embolism and thrombosis of unspecified deep veins of proximal lower extremity, bilateral
I82.5Y9	Chronic embolism and thrombosis of unspecified deep veins of unspecified proximal lower extremity
I82.5Z	Chronic embolism and thrombosis of unspecified deep veins of distal lower extremity
I82.5Z1	Chronic embolism and thrombosis of unspecified deep veins of right distal lower extremity
182.5Z2	Chronic embolism and thrombosis of unspecified deep veins of left distal lower extremity
182.5Z3	Chronic embolism and thrombosis of unspecified deep veins of distal lower extremity, bilateral
182.529	Chronic embolism and thrombosis of unspecified deep veins of unspecified distal lower extremity
182.6	Acute embolism and thrombosis of veins of upper extremity
182.60	Acute embolism and thrombosis of unspecified veins of upper extremity
182.601	Acute embolism and thrombosis of unspecified veins of right upper extremity
182.602	Acute embolism and thrombosis of unspecified veins of left upper extremity
182.603	Acute embolism and thrombosis of unspecified veins of upper extremity, bilateral
182.609	Acute embolism and thrombosis of unspecified veins of unspecified upper extremity
182.62	Acute embolism and thrombosis of deep veins of upper extremity
182.621	Acute embolism and thrombosis of deep veins of right upper extremity
182.622	Acute embolism and thrombosis of deep veins of left upper extremity
182.623	Acute embolism and thrombosis of deep veins of upper extremity, bilateral

182.629	Acute embolism and thrombosis of deep veins of unspecified upper extremity
182.890	Acute embolism and thrombosis of other specified veins
182.90	Acute embolism and thrombosis of unspecified vein
I82.A1	Acute embolism and thrombosis of axillary vein
I82.A11	Acute embolism and thrombosis of right axillary vein
I82.A12	Acute embolism and thrombosis of left axillary vein
I82.A13	Acute embolism and thrombosis of axillary vein, bilateral
I82.A19	Acute embolism and thrombosis of unspecified axillary vein
I82.B1	Acute embolism and thrombosis of subclavian vein
I82.B11	Acute embolism and thrombosis of right subclavian vein
I82.B12	Acute embolism and thrombosis of left subclavian vein
I82.B13	Acute embolism and thrombosis of subclavian vein, bilateral
I82.B19	Acute embolism and thrombosis of unspecified subclavian vein
I82.C1	Acute embolism and thrombosis of internal jugular vein
I82.C11	Acute embolism and thrombosis of right internal jugular vein
I82.C12	Acute embolism and thrombosis of left internal jugular vein
I82.C13	Acute embolism and thrombosis of internal jugular vein, bilateral
I82.C19	Acute embolism and thrombosis of unspecified internal jugular vein

Title	
Major Bleeding	
, , ,	
ICD-9 Dx: 1 inpatient or 2 outpatient	
562.02	DIVERTICULOSIS OF SMALL INTESTINE WITH HEMORRHAGE
562.03	DIVERTICULITIS OF SMALL INTESTINE WITH HEMORRHAGE
562.12	DIVERTICULOSIS OF COLON WITH HEMORRHAGE
562.13	DIVERTICULITIS OF COLON WITH HEMORRHAGE
568.81	HEMOPERITONEUM (NONTRAUMATIC
569.3	HEMORRHAGE OF RECTUM AND ANUS
569.83	PERFORATION OF INTESTINE
569.85	ANGIODYSPLASIA OF INTESTINE WITH HEMORRHAGE OF INTESTINE
569.86	DIEULAFOY LESION (HEMORRHAGIC
578	HEMATEMESIS
578.9	HEMORRHAGE OF GASTROINTESTINAL TRACT UNSPECIFIED
423	HEMOPERICARDIUM
432	NONTRAUMATIC EXTRADURAL HEMORRHAGE
432.1	SUBDURAL HEMORRHAGE
432.9	UNSPECIFIED INTRACRANIAL HEMORRHAGE
459	HEMORRHAGE UNSPECIFIED
531	ACUTE GASTRIC ULCER WITH HEMORRHAGE
531	ACUTE GASTRIC ULCER WITH HEMORRHAGE WITHOUT OBSTRUCTION
531.01	ACUTE GASTRIC ULCER WITH HEMORRHAGE WITH OBSTRUCTION
531.2	ACUTE GASTRIC ULCER WITH HEMORRHAGE AND PERFORATION
531.2	ACUTE GASTRIC ULCER WITH HEMORRHAGE AND PERFORATION WITHOUT OBSTRUCTION
531.21	ACUTE GASTRIC ULCER WITH HEMORRHAGE AND PERFORATION WITH OBSTRUCTION
531.4	CHRONIC OR UNSPECIFIED GASTRIC ULCER WITH HEMORRHAGE
531.4	CHRONIC OR UNSPECIFIED GASTRIC ULCER WITH HEMORRHAGE WITHOUT OBSTRUCTION
531.41	CHRONIC OR UNSPECIFIED GASTRIC ULCER WITH HEMORRHAGE WITH OBSTRUCTION
531.6	CHRONIC OR UNSPECIFIED GASTRIC ULCER WITH HEMORRHAGE AND PERFORATION
531.6	CHRONIC OR UNSPECIFIED GASTRIC ULCER WITH HEMORRHAGE AND PERFORATION WITHOUT OBSTRUCTION
531.61	CHRONIC OR UNSPECIFIED GASTRIC ULCER WITH HEMORRHAGE AND PERFORATION WITH OBSTRUCTION
532	ACUTE DUODENAL ULCER WITH HEMORRHAGE
532	ACUTE DUODENAL ULCER WITH HEMORRHAGE WITHOUT OBSTRUCTION
532.01	ACUTE DUODENAL ULCER WITH HEMORRHAGE WITH OBSTRUCTION
532.2	ACUTE DUODENAL ULCER WITH HEMORRHAGE AND PERFORATION
532.2	ACUTE DUODENAL ULCER WITH HEMORRHAGE AND PERFORATION WITHOUT OBSTRUCTION
532.21	ACUTE DUODENAL ULCER WITH HEMORRHAGE AND PERFORATION WITH OBSTRUCTION
532.4	CHRONIC OR UNSPECIFIED DUODENAL ULCER WITH HEMORRHAGE
532.4	CHRONIC OR UNSPECIFIED DUODENAL ULCER WITH HEMORRHAGE WITHOUT OBSTRUCTION
532.41	CHRONIC OR UNSPECIFIED DUODENAL ULCER WITH HEMORRHAGE WITH OBSTRUCTION

532.6	CHRONIC OR UNSPECIFIED DUODENAL ULCER WITH HEMORRHAGE AND PERFORATION
532.6	CHRONIC OR UNSPECIFIED DUODENAL ULCER WITH HEMORRHAGE AND PERFORATION WITHOUT OBSTRUCTION
532.61	CHRONIC OR UNSPECIFIED DUODENAL ULCER WITH HEMORRHAGE AND PERFORATION WITH OBSTRUCTION
533	ACUTE PEPTIC ULCER OF UNSPECIFIED SITE WITH HEMORRHAGE
533	ACUTE PEPTIC ULCER OF UNSPECIFIED SITE WITH HEMORRHAGE WITHOUT OBSTRUCTION
533.01	ACUTE PEPTIC ULCER OF UNSPECIFIED SITE WITH HEMORRHAGE WITH OBSTRUCTION
533.2	ACUTE PEPTIC ULCER OF UNSPECIFIED SITE WITH HEMORRHAGE AND PERFORATION
533.2	ACUTE PEPTIC ULCER OF UNSPECIFIED SITE WITH HEMORRHAGE AND PERFORATION WITHOUT OBSTRUCTION
533.21	ACUTE PEPTIC ULCER OF UNSPECIFIED SITE WITH HEMORRHAGE AND PERFORATION WITH OBSTRUCTION
533.4	CHRONIC OR UNSPECIFIED PEPTIC ULCER OF UNSPECIFIED SITE WITH HEMORRHAGE
533.4	CHRONIC OR UNSPECIFIED PEPTIC ULCER OF UNSPECIFIED SITE WITH HEMORRHAGE WITHOUT OBSTRUCTION
533.41	CHRONIC OR UNSPECIFIED PEPTIC ULCER OF UNSPECIFIED SITE WITH HEMORRHAGE WITH OBSTRUCTION
533.6	CHRONIC OR UNSPECIFIED PEPTIC ULCER OF UNSPECIFIED SITE WITH HEMORRHAGE AND PERFORATION
533.6	CHRONIC OR UNSPECIFIED PEPTIC ULCER OF UNSPECIFIED SITE WITH HEMORRHAGE AND PERFORATION WITHOUT OBSTRUCTION
533.61	CHRONIC OR UNSPECIFIED PEPTIC ULCER OF UNSPECIFIED SITE WITH HEMORRHAGE AND PERFORATION WITH OBSTRUCTION
534	ACUTE GASTROJEJUNAL ULCER WITH HEMORRHAGE
534	ACUTE GASTROJEJUNAL ULCER WITH HEMORRHAGE WITHOUT OBSTRUCTION
534.01	ACUTE GASTROJEJUNAL ULCER WITH HEMORRHAGE WITH OBSTRUCTION
534.2	ACUTE GASTROJEJUNAL ULCER WITH HEMORRHAGE AND PERFORATION
534.2	ACUTE GASTROJEJUNAL ULCER WITH HEMORRHAGE AND PERFORATION WITHOUT OBSTRUCTION
534.21	ACUTE GASTROJEJUNAL ULCER WITH HEMORRHAGE AND PERFORATION WITH OBSTRUCTION
534.4	CHRONIC OR UNSPECIFIED GASTROJEJUNAL ULCER WITH HEMORRHAGE
534.4	CHRONIC OR UNSPECIFIED GASTROJEJUNAL ULCER WITH HEMORRHAGE WITHOUT OBSTRUCTION
534.41	CHRONIC OR UNSPECIFIED GASTROJEJUNAL ULCER WITH HEMORRHAGE WITH OBSTRUCTION
534.6	CHRONIC OR UNSPECIFIED GASTROJEJUNAL ULCER WITH HEMORRHAGE AND PERFORATION
534.6	CHRONIC OR UNSPECIFIED GASTROJEJUNAL ULCER WITH HEMORRHAGE AND PERFORATION WITHOUT OBSTRUCTION
534.61	CHRONIC OR UNSPECIFIED GASTROJEJUNAL ULCER WITH HEMORRHAGE AND PERFORATION WITH OBSTRUCTION
578.1	BLOOD IN STOOL
719.1	HEMARTHROSIS
719.1	HEMARTHROSIS SITE UNSPECIFIED
719.11	HERARTHROSIS INVOLVING SHOULDER REGION
719.12	HEMARTHORSIS INVOLVING UPPER ARM
719.13	HEMARTHROSIS INVOLVING FOREARM
719.14	HEMARTHROSIS INVOLVING HAND
719.15	HEMARTHROSIS INVOLVING PELVIC REGION AND THIGH
719.16	HEMARTHROSIS INVOLVING LOWER LEG
719.17	HEMARTHROSIS INVOLVING ANKLE AND FOOT
719.18	HEMARTHROSIS INVOLVING OTHER SPECIFIED SITES
719.19	HEMARTHROSIS INVOLVING MULTIPLE SITES
430	SUBARACHNOID HEMORRHAGE
431	INTRACEREBRAL HEMORRHAGE

784.7	EPISTAXIS
784.8	HEMORRHAGE FROM THROAT
599.7	HEMATURIA
599.7	HEMATURIA UNSPECIFIED
599.71	GROSS HEMATURIA
599.72	MICROSCOPIC HEMATURIA
786.3	HEMOPTYSIS
786.3	HEMOPTYSIS UNSPECIFIED
786.31	ACUTE IDIOPATHIC PULMONARY HEMORRHAGE IN INFANTS
786.39	OTHER HEMOPTYSIS
,	
ICD-10 Dx: 1 inpatient or 2 outpatient	
131.2	Hemopericardium, not elsewhere classified
160.00	Nontraumatic subarachnoid hemorrhage from unspecified carotid siphon and bifurcation
160.01	Nontraumatic subarachnoid hemorrhage from right carotid siphon and bifurcation
160.02	Nontraumatic subarachnoid hemorrhage from left carotid siphon and bifurcation
160.10	Nontraumatic subarachnoid hemorrhage from unspecified middle cerebral artery
160.11	Nontraumatic subarachnoid hemorrhage from right middle cerebral artery
160.12	Nontraumatic subarachnoid hemorrhage from left middle cerebral artery
160.2	Nontraumatic subarachnoid hemorrhage from anterior communicating artery
160.30	Nontraumatic subarachnoid hemorrhage from unspecified posterior communicating artery
160.31	Nontraumatic subarachnoid hemorrhage from right posterior communicating artery
160.32	Nontraumatic subarachnoid hemorrhage from left posterior communicating artery
160.4	Nontraumatic subarachnoid hemorrhage from basilar artery
160.50	Nontraumatic subarachnoid hemorrhage from unspecified vertebral artery
160.51	Nontraumatic subarachnoid hemorrhage from right vertebral artery
160.52	Nontraumatic subarachnoid hemorrhage from left vertebral artery
160.6	Nontraumatic subarachnoid hemorrhage from other intracranial arteries
160.7	Nontraumatic subarachnoid hemorrhage from unspecified intracranial artery
160.8	Other nontraumatic subarachnoid hemorrhage
160.9	Nontraumatic subarachnoid hemorrhage, unspecified
161.0	Nontraumatic intracerebral hemorrhage in hemisphere, subcortical
161.1	Nontraumatic intracerebral hemorrhage in hemisphere, cortical
161.2	Nontraumatic intracerebral hemorrhage in hemisphere, unspecified
161.3	Nontraumatic intracerebral hemorrhage in brain stem
161.4	Nontraumatic intracerebral hemorrhage in cerebellum
161.5	Nontraumatic intracerebral hemorrhage, intraventricular
161.6	Nontraumatic intracerebral hemorrhage, multiple localized
161.8	Other nontraumatic intracerebral hemorrhage
161.9	Nontraumatic intracerebral hemorrhage, unspecified
162.00	Nontraumatic subdural hemorrhage, unspecified

162.01	Nontraumatic acute subdural hemorrhage
162.02	Nontraumatic subacute subdural hemorrhage
162.03	Nontraumatic chronic subdural hemorrhage
162.1	Nontraumatic extradural hemorrhage
162.9	Nontraumatic intracranial hemorrhage, unspecified
K25.0	Acute gastric ulcer with hemorrhage
K25.2	Acute gastric ulcer with both hemorrhage and perforation
K25.4	Chronic or unspecified gastric ulcer with hemorrhage
K25.6	Chronic or unspecified gastric ulcer with both hemorrhage and perforation
K26.0	Acute duodenal ulcer with hemorrhage
K26.2	Acute duodenal ulcer with both hemorrhage and perforation
K26.4	Chronic or unspecified duodenal ulcer with hemorrhage
K26.6	Chronic or unspecified duodenal ulcer with both hemorrhage and perforation
K27.0	Acute peptic ulcer, site unspecified, with hemorrhage
K27.2	Acute peptic ulcer, site unspecified, with both hemorrhage and perforation
K27.4	Chronic or unspecified peptic ulcer, site unspecified, with hemorrhage
K27.6	Chronic or unspecified peptic ulcer, site unspecified, with both hemorrhage and perforation
K28.0	Acute gastrojejunal ulcer with hemorrhage
K28.2	Acute gastrojejunal ulcer with both hemorrhage and perforation
K28.4	Chronic or unspecified gastrojejunal ulcer with hemorrhage
K28.6	Chronic or unspecified gastrojejunal ulcer with both hemorrhage and perforation
K55.21	Angiodysplasia of colon with hemorrhage
K56.60	Unspecified intestinal obstruction
K57.01	Diverticulitis of small intestine with perforation and abscess with bleeding
K57.11	Diverticulosis of small intestine without perforation or abscess with bleeding
K57.13	Diverticulitis of small intestine without perforation or abscess with bleeding
K57.21	Diverticulitis of large intestine with perforation and abscess with bleeding
K57.31	Diverticulosis of large intestine without perforation or abscess with bleeding
K57.33	Diverticulitis of large intestine without perforation or abscess with bleeding
K57.41	Diverticulitis of both small and large intestine with perforation and abscess with bleeding
K57.51	Diverticulosis of both small and large intestine without perforation or abscess with bleeding
K57.53	Diverticulitis of both small and large intestine without perforation or abscess with bleeding
K57.81	Diverticulitis of intestine, part unspecified, with perforation and abscess with bleeding
K57.91	Diverticulosis of intestine, part unspecified, without perforation or abscess with bleeding
K57.93	Diverticulitis of intestine, part unspecified, without perforation or abscess with bleeding
K62.5	Hemorrhage of anus and rectum
K63.1	Perforation of intestine (nontraumatic
K63.81	Dieulafoy lesion of intestine
K66.1	Hemoperitoneum
К92.0	Hematemesis
К92.1	Melena

К92.2	Gastrointestinal hemorrhage, unspecified
M25.00	Hemarthrosis, unspecified joint
M25.011	Hemarthrosis, right shoulder
M25.012	Hemarthrosis, left shoulder
M25.019	Hemarthrosis, unspecified shoulder
M25.021	Hemarthrosis, right elbow
M25.022	Hemarthrosis, left elbow
M25.029	Hemarthrosis, unspecified elbow
M25.031	Hemarthrosis, right wrist
M25.032	Hemarthrosis, left wrist
M25.039	Hemarthrosis, unspecified wrist
M25.041	Hemarthrosis, right hand
M25.042	Hemarthrosis, left hand
M25.049	Hemarthrosis, unspecified hand
M25.051	Hemarthrosis, right hip
M25.052	Hemarthrosis, left hip
M25.059	Hemarthrosis, unspecified hip
M25.061	Hemarthrosis, right knee
M25.062	Hemarthrosis, left knee
M25.069	Hemarthrosis, unspecified knee
M25.071	Hemarthrosis, right ankle
M25.072	Hemarthrosis, left ankle
M25.073	Hemarthrosis, unspecified ankle
M25.074	Hemarthrosis, right foot
M25.075	Hemarthrosis, left foot
M25.076	Hemarthrosis, unspecified foot
M25.08	Hemarthrosis, other specified site
R58	Hemorrhage, not elsewhere classified
R04	Hemorrhage from respiratory passages
R04.0	Epistaxis
R04.1	Hemorrhage from throat
R04.2	Hemoptysis
R04.8	Hemorrhage from other sites in respiratory passages
R04.81	Acute idiopathic pulmonary hemorrhage in infants
R04.89	Hemorrhage from other sites in respiratory passages
R04.9	Hemorrhage from respiratory passages, unspecified
R31	Hematuria
R31.0	Gross hematuria
R31.1	Benign essential microscopic hematuria
R31.2	Other microscopic hematuria
R31.21	Asymptomatic microscopic hematuria

R31.29	Other microscopic hematuria
R31.9	Hematuria, unspecified
ICD-9 Px	
44.43	ENDOSCOPIC CONTROL OF GASTRIC OF DUODENAL BLEEDING
ICD-10 Px	
0W3P8ZZ	Control Bleeding in Gastrointestinal Tract, Via Natural or Artificial Opening Endoscopic
HCPCS	
43255	Esophagogastroduodenoscopy, flexible, transoral; with control of bleeding, any method / Upper gastrointestinal endoscopy including esophagus, stomach, and either the duodenum and/or jejunum as appropriate; with control of bleeding, any method

	Pregnancy
Dx codes	
650 NORMAL DELIVERY	
660 OBSTRUCTED LABC	IR
661 ABNORMALITY OF F	-ORCES OF LABOR
662 LONG LABOR	
663 UMBILICAL CORD C	COMPLICATIONS DURING LABOR AND DELIVERY
664 TRAUMA TO PERINI	EUM AND VULVA DURING DELIVERY
665 OTHER OBSTETRICA	AL TRAUMA
667 RETAINED PLACENT	TA OR MEMBRANES WITHOUT HEMORRHAGE
668 COMPLICATIONS O	F THE ADMINISTRATION OF ANESTHETIC OR OTHER SEDATION IN LABOR AND DELIVERY
669.94 UNSPECIFIED C	OMPLICATION OF LABOR AND DELIVERY POSTPARTUM CONDITION OR COMPLICATION
V24 POSTPARTUM CAR	E AND EXAMINATION
V24.0 POSTPARTUM CA	RE AND EXAMINATION IMMEDIATELY AFTER DELIVERY
V24.1 POSTPARTUM CA	ARE AND EXAMINATION OF LACTATING MOTHER
V24.2 ROUTINE POSTPA	ARTUM FOLLOW
V27 OUTCOME OF DELI	VERY
V27.0 MOTHER WITH SI	INGLE LIVEBORN
V27.1 MOTHER WITH SI	NGLESTILLBORN
V27.2 MOTHER WITH T	WINS BOTH LIVEBORN
V27.3 MOTHER WITH T	WINS ONE LIVEBORN AND ONE STILLBORN
V27.4 MOTHER WITH T	WINS BOTH STILLBORN
V27.5 MOTHER WITH O	ITHER MULTIPLE BIRTH ALL LIVEBORN
V27.6 MOTHER WITH O	THER MULTIPLE BIRTH SOME LIVEBORN
V27.7 MOTHER WITH O	THER MULTIPLE BIRTH ALL STILLBORN
V27.9 MOTHER WITH U	NSPECIFIED OUTCOME OF DELIVERY
Procedure codes	
72.0 LOW FORCEPS OP	ERATION
72.1 LOW FORCEPS OP	ERATION WITH EPISIOTOMY
72.2 MID FORCEPS OPE	RATION
72.21 MID FORCEPS OP	PERATION WITH EPISIOTOMY
72.29 OTHER MID FORC	CEPS OPERATION
72.3 HIGH FORCEPS OP	ERATION
72.31 HIGH FORCEPS O	PERATION WITH EPISIOTOMY
72.39 OTHER HIGH FOR	CEPS OPERATION

72.4 FORCEPS ROTATION OF FETAL HEAD 72.5 BREECH EXTRACTION 72.51 PARTIAL BREECH EXTRACTION WITH FORCEPS TO AFTERCOMING HEAD 72.52 OTHER PARTIAL BREECH EXTRACTION 72.53 TOTAL BREECH EXTRACTION WITH FORCEPS TO AFTERCOMING HEAD 72.54 OTHER TOTAL BREECH EXTRACTION 72.6 FORCEPS APPLICATION TO AFTERCOMING HEAD 72.7 VACUUM EXTRACTION 72.71 VACUUM EXTRACTION WITH EPISIOTOMY 72.79 OTHER VACUUM EXTRACTION 72.8 OTHER SPECIFIED INSTRUMENTAL DELIVERY 72.9 UNSPECIFIED INSTRUMENTAL DELIVERY 73.0 ARTIFICIAL RUPTURE OF MEMBRANES 73.01 INDUCTION OF LABOR BY ARTIFICIAL RUPTURE OF MEMBRANES 73.09 OTHER ARTIFICIAL RUPTURE OF MEMBRANES 73.1 OTHER SURGICAL INDUCTION OF LABOR 73.2 INTERNAL AND COMBINED VERSION AND EXTRACTION 73.21 INTERNAL AND COMBINED VERSION WITHOUT EXTRACTION 73.22 INTERNAL AND COMBINED VERSION WITH EXTRACTION 73.3 FAILED FORCEPS 73.4 MEDICAL INDUCTION OF LABOR 73.5 MANUALLY ASSISTED DELIVERY 73.51 MANUAL ROTATION OF FETAL HEAD 73.59 OTHER MANUALLY ASSISTED DELIVERY 73.6 EPISIOTOMY 73.8 OPERATIONS ON FETUS TO FACILITATE DELIVERY 73.9 OTHER OPERATIONS ASSISTING DELIVERY 73.91 EXTERNAL VERSION ASSISTING DELIVERY 73.92 REPLACEMENT OF PROLAPSED UMBILICAL CORD 73.93 INCISION OF CERVIX TO ASSIST DELIVERY 73.94 PUBIOTOMY TO ASSIST DELIVERY 73.99 OTHER OPERATIONS ASSISTING DELIVERY 74.0 CLASSICAL CESAREAN SECTION 74.1 LOW CERVICAL CESAREAN SECTION 74.2 EXTRAPERITONEAL CESAREAN SECTION

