# 1.4 Required power for primary endpoint and noninferiority margin (if applicable) Assuming a noninferiority margin of 2.0, it was determined that about 3,000 patients would be needed to achieve 90% power to conclude noninferiority of rivaroxaban over standard therapy at two-sided alpha of 0.05.

1.5 Secondary endpoint for replication (assay sensitivity) and RCT finding Major bleeding; RR = 0.65 (95% CI 0.33–1.30)

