### 14.5 Table 5: Results from secondary analyses;

### 15. References

#	EINSTEIN DVT trial definitions	Implementation in routine care	Please see the following Google Drive for further details or any missing infor https://drive.google.com/drive/folders/1WD618wrywYIEaXrlLTcuK-VCcnb6b-gV7	mation: usp=sharing
	Trial details- Primary approval; Unintended S with label change		Some codes are not listed in this document because of excel cell size limitations and excessive number of ICD-10 codes. Full ICD-10 code lists will be available in the above Google Drive Folder (link above). ICD-9 to ICD-10 code conversions were completed using a SAS macro that implements. forward/backward mapping based on the CMS ICD-9 to ICD-10 mapping: https://www.nber.ore/data/cd9-icd-10-cm-and-pcs-crosswalk-general-gouvalence-mapping.html	
	EXPOSURE vs. COMPARISON		References/Rationale	Color coding
		Rivaroxaban vs. Warfarin		Criteria
	PRIM	ARY OUTCOME		Adequate mapping in claims
	Recurrent thromboembolism defined as the composite of (Deep vein thrombosis) DVT or nonfatal or fatal pulmonary embolism (PE)	Measured 1 day after drug initiation in any diagnosis position and in an inpatient care setting Recurrent VTE (composite of DVT or PE); See 'VTE' sheet for codes	Fang MC, Fan D, Sung SH, et al. Validity of Using Inpatient and Outpatient Administrative Codes to Identify Acute Venous Thromboembolism: The CVRN VTE Study. Med Care. 2017;55(12):e137-e143.	Intermediate mapping in claims
				Poor mapping or cannot be measured

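### The only printed bleeding definition accepts two outpatient claims for epistaxis, blood in stool or hematuria; if it defines the safety outcome, minor bleeds count as major

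*Combined protocol and SAP*

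**What the plan says.** Section 6.3.1 lists major bleeding as the only safety outcome and gives no care setting, code list or sheet reference beside it. Section 1.5 names it as the secondary (assay-sensitivity) endpoint and gives the trial result, "Major bleeding; RR = 0.65" with a 95% CI of 0.33–1.30. It does not give the trial's definition of a major bleed.

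Appendix A contains one bleeding definition, the Major Bleeding sheet. Its diagnosis lists are headed "ICD-9 Dx: 1 inpatient or 2 outpatient" and "ICD-10 Dx: 1 inpatient or 2 outpatient". Among the codes under those headings are:

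- 578.1, "BLOOD IN STOOL"
- 784.7 and R04.0, epistaxis
- 599.7, 599.71 and 599.72, hematuria, the last being "MICROSCOPIC HEMATURIA"
- R31.21, "Asymptomatic microscopic hematuria"
- K56.60, "Unspecified intestinal obstruction", which is not a bleed by its own label

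The sheet's procedure codes stand under separate headings with no setting rule. The sheet is cited by name once, for Exclusion 10 (active bleeding or bleeding history in the 180 days up to and including drug initiation).

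The primary VTE outcome, by contrast, is "Measured 1 day after drug initiation in any diagnosis position and in an inpatient care setting". The VTE sheet's headers differ from that row on diagnosis position but also require an inpatient claim.

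**The concern.** A broad rule suits a baseline exclusion, where the aim is to remove anyone with a possible bleeding history. It suits an outcome called major bleeding much less well. Taken literally, two outpatient claims for a symptomless urine finding would be a major event. A ratio estimate depends on specificity: events that are not major bleeds, and that do not respond to treatment as major bleeds do, move the HR toward their own HR. The safety HR will be set beside the trial's 0.65, so a null-looking result could come from the definition and not from the drugs.

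The two-claim rule also fits poorly with as-treated follow-up (Section 6.3.2), which ends 10 days after the supply runs out or at a switch. The plan does not say which claim dates the event, how far apart the two may be, or whether the second must fall before censoring. If a bleed leads to stopping the drug, the confirming claim may come after follow-up has ended.

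**Working it through.** **Plan figures.** The only power figures are for VTE, and they reproduce. Pooled events are 25,970 × 18.54/1,000 = 481.48. Power for HR 0.68 at two-sided 0.05 with 1:1 allocation is Φ(√(481.48/4) × |ln 0.68| − 1.96) = Φ(2.27) = 0.988, as stated in Section 10. None of this depends on the bleeding definition. No bleeding count, rate or power is stated.

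**What is known about events on the sheet.** Exclusion 10 (Section 5.3) removed:

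- Optum: 295 of 12,068 (2.4%)
- MarketScan: 478 of 19,324 (2.5%)
- Medicare: 1,156 of 51,723 (2.2%)
- Total: 1,929 of 83,115 (2.3%)

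These counts are not split by code or by care setting, so the share due to outpatient epistaxis, hematuria or blood in stool cannot be computed.

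**Illustration of dilution.** Assume a true major-bleeding HR of 0.65 and an HR of 1 for the added minor events. Let f be the share of referent-arm counted events that are minor; f is not in the documents. Then

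HR observed = f × 1 + (1 − f) × 0.65 = 0.65 + 0.35f.

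The events needed for 80% power at two-sided 0.05 with 1:1 allocation come from 4 × (1.96 + 0.8416)² / (ln HR)².

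| f | HR observed | Events for 80% power |
|---|---|---|
| 0% | 0.65 | 170 |
| 10% | 0.685 | 220 |
| 25% | 0.7375 | 339 |
| 50% | 0.825 | 849 |
| 75% | 0.9125 | 3,745 |

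At f = 80% the HR is 0.65 + 0.28 = 0.93.

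The meaning of f matters. Suppose it is instead the share of all counted events in two equal arms. With m minor events per arm and M major referent events, f = 2m/(2m + 1.65M) and HR = (m + 0.65M)/(m + M). At f = 50%, m = 0.825M and HR = 1.475/1.825 = 0.81. At f = 80%, m = 3.3M and HR = 3.95/4.3 = 0.92.

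**Precision of the benchmark.** SE(log RR) = (ln 1.30 − ln 0.33)/(2 × 1.96) = 0.35. On the 4/SE² approximation that is about 33 events.

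**Follow-up available for a second claim.** Section 9 gives median follow-up in days for rivaroxaban and warfarin as 54 and 64 (Optum), 67 and 78 (MarketScan), and 65 and 82 (Medicare). Follow-up is short in both arms and shorter on rivaroxaban in all three databases. If the second claim must fall within follow-up, there is less time for it in the exposed arm. If it need not, event status depends on data after censoring. The plan does not say which applies.

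**The case against.** The strongest reply is that the sheet is never assigned to the outcome. Its one citation is Exclusion 10, and the same setting rule is used in Appendix B for baseline hypertension, diabetes and intracranial or retroperitoneal hemorrhage. The one sheet explicitly cited for an outcome, the VTE sheet, is inpatient only. The rule may therefore be a baseline rule, and Appendix A points to an external folder for further detail. This stands as a caveat: outcome use is an inference. It is a strong one, because the sheet's title matches the outcome's name and no other bleeding definition is printed. If the inference is wrong, the sole safety outcome has no printed definition, which also needs correcting.

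A reader might also infer stronger conclusions that the documents do not support:

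- *The result is not comparable with the trial's major bleeding.* The trial's definition is not given, so one can say only that comparability is not established. The diluted values above also all lie inside the trial's own CI.
- *The safety HR would mostly reflect minor bleeding.* No split by code or setting exists, so f is unknown.
- *Every code on the sheet is affected.* The procedure codes carry no setting rule.
- *Requiring admission for VTE but not for bleeding biases the comparison.* Each HR compares arms within one endpoint, so the difference is an unexplained inconsistency and not a bias in either HR.
- *Unequal clinic contact causes detection bias.* This is possible, but no data on visits during follow-up are given.

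Finally, an inpatient rule alone would still admit an inpatient code for microscopic hematuria. That is correct, and it is why the code list has to be trimmed as well.

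**Conclusion.** The point holds on the condition that the Major Bleeding sheet defines the safety outcome, which is the natural reading of the plan. On that reading, two outpatient diagnosis claims for a minor or symptomless finding count as a major bleed, the HR could be drawn toward 1, and the reading against RR 0.65 is not secured. The size cannot be computed from the documents. The figures of 0.825 and 0.93 are illustrations that rest on an assumed share of minor referent-arm events and an assumed HR of 1 for them. The unstated gap and event-date rules, with short as-treated follow-up, are a separate weakness that does not depend on the trial's definition. The primary VTE analysis is unaffected. The change should be made before the comparative analyses; Section 13, where they are to be recorded, is still blank.

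**What to change.** - Define the major-bleeding outcome in its own Appendix A row, separate from Exclusion 10.
- For the outcome, require an inpatient diagnosis claim dated within follow-up. State the diagnosis position, and whether and how the procedure codes count.
- Drop codes that are not major bleeds by their own label, such as microscopic hematuria and K56.60.
- Keep the rule of one inpatient or two outpatient claims for baseline bleeding history.
- Report the broad list as a separately named any-bleeding outcome, with the maximum gap between claims, the event date and the handling of a second claim after censoring all stated.

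The cost is one definition change, fewer safety events and a wider CI. A narrower definition gives up some sensitivity, and the any-bleeding outcome keeps that information visible. Comparability with the trial would still need the trial's own bleeding definition set beside the new one.
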